#### **5.2.4      Eastern Cooperative Oncology Group (ECOG) Performance Status**

The Eastern Cooperative Oncology Group (ECOG) Performance Status will be used to assess patients' performance status ([Table 3](#)).

**Table 3            ECOG Performance Status**

#### **ECOG PERFORMANCE STATUS**

Grade	ECOG
0	Fully active, able to carry on all pre-disease performance without restriction
1	Restricted in physically strenuous activity but ambulatory and able to carry out work of a light or sedentary nature, e.g., light house work, office work
2	Ambulatory and capable of all self-care but unable to carry out any work activities. Up and about more than 50% of waking hours
3	Capable of only limited self-care, confined to bed or chair more than 50% of waking hours
4	Completely disabled. Cannot carry on any self-care. Totally confined to bed or chair
5	Dead

#### **5.2.5      Vital signs**

Vital signs will be measured at all study visits and will include heart rate, respiratory rate, temperature, and blood pressure (systolic and diastolic). Blood pressure and heart rate will be done at rest as per standard practice at the investigational site. Significant findings noticed after the start of investigational product and findings that worsen significantly, which meet the definition of an AE must be recorded on the AE eCRF.

#### **5.2.6      ECG**

Single 12-lead ECG will be obtained using a centrally provided calibrated ECG machine that automatically calculates the heart rate and measures PR, QRS, QT, and QTc intervals. Triplicate ECGs, at least 3 minutes apart, will be performed if QTcF is > 500 msec or if the Investigator identifies an ECG finding (for example QT interval prolonged or cardiac arrhythmia) that is an adverse event and related to investigational product. Additional timepoints may be added, as clinically indicated.

Patients should be in the supine position after the patient has rested for at least 5 minutes. In the event of possible ECG findings, additional ECG reads could be added at follow-up visits. The ECG evaluation will be performed centrally. Clinically significant ECG abnormalities will be recorded on the eCRF.

Confidential

Document State: Effective (Controlled)  
CONFIDENTIAL

Page 45 of 118

## 5.2.7 Physical examination

The complete physical examination will include appearance, eyes, ears, nose, head, throat, neck, lungs, heart, abdomen, extremities, skin, and musculoskeletal system.

Treatment directed physical examination, will be conducted as outlined in the SoA (Table 1).

Significant findings made after the start of investigational product which meet the definition of an AE must be recorded on the AE eCRF.

Height will be recorded at Screening and weight measurements using a medical scale will be recorded as outlined in the SoA (Table 1).

## 5.2.8 Safety Laboratory Assessments

Safety laboratory assessments for this study are to be performed by local laboratory at times designated in the SoA Screening laboratory results may be used for C1D1 if conducted within 3-7 days.

Findings that worsen significantly after the start of investigational product which meet the definition of an AE per the Investigator's discretion must be recorded on the AE eCRF (refer to Section 8.1).

The laboratory evaluations will include, but not limited to:

- Hematology/CBC including hemoglobin, hematocrit, platelet count, white blood cell (WBC) count, and absolute differential count
- Peripheral blood lymphocytes subsets; this may include percent of B cells, T cells, NK cell, T-Helper cells, T cytotoxic (killer) cells, T reg (suppressor) cells and macrophages. Blood will be collected and analyzed locally per available flow panels. Sites are allowed to leave the eCRF blank for any subsets not included in their standard evaluation panel.
- Serum chemistry: Glucose, blood Urea Nitrogen (BUN), creatinine, total bilirubin, albumin, aspartate aminotransferase (AST), alanine aminotransferase (ALT), alkaline phosphatase, lactate dehydrogenase (LDH), and electrolytes (sodium, potassium, chloride, calcium, magnesium, and phosphorus). A direct bilirubin should be obtained if the total bilirubin level is >1.5 times ULN. Creatinine clearance will be done at Screening only.
- Triglycerides
- Hemoglobin A1c
- Thyroid function: Thyroid stimulating hormone (TSH), total T3 and free T4
- Coagulation assessment, including: prothrombin time (PT), and activated partial thromboplastin time (aPTT).
- Serology: HIV, HBsAg, HCV RNA (qualitative).
- Prostate-specific antigen (PSA) (male only)

Confidential

- Urinalysis (dipstick): pH, glucose, ketones, protein, specific gravity, bilirubin and evidence of infection; microscopic examination will be done when findings are abnormal.
- Lipase – only for patients who experience  $\geq$  Grade 2 diarrhea

All safety laboratories, hematology, chemistry and urine analysis are to be drawn by standard phlebotomy techniques, into the site prescribed appropriate tubes for the specific tests and amounts prescribed by local laboratory, e.g., CBC with differential 5 ml in a purple top tube., chemistry 10 ml in a red top tube. Refer to the Laboratory Manual for further details on specimen collection and handling procedures.

### **5.2.9      Pregnancy Test**

Women of childbearing potential will have a urine or serum pregnancy test at timepoints designated in the SoA.

### **5.3           POPULATION PHARMACOKINETICS**

Blood samples for population pharmacokinetics (PK) will be obtained at the times designated in the SoA, footnote q (Table 1). Start- and end-time for each investigational product infusion (and any interruptions) will be recorded in the eCRF. The actual time of the sample collection will be recorded in the eCRF. All samples will be analyzed for both parent and metabolite using liquid chromatography with tandem mass spectrometry (LC-MS/MS) assay.

A population (mixed-effects) approach will be used to analyze the concentration data, the goal being to obtain a set of population parameters and to identify covariates that affect systemic exposure to each of the parent and metabolite. For each of parent and metabolite, one- and two-compartment linear models will be applied to the data. If graphics suggest that these models are not appropriate, other models such as those including non-linearity with respect to dose and/or time will be evaluated. The relationship of pharmacokinetic parameters to body size will be evaluated systematically. Other covariates will be considered for inclusion in the model based on graphics. Models will be selected based on graphics and changes in the objective function. The analysis will be conducted with NONMEM software.

For more details on instructions for collecting PK samples, refer to the Study PK Manual.

### **5.4           BIOMARKERS**

Notch mutational status from prior tests with any commercially available NGS assay kit or as assessed at enrollment by institutional NGS test will be confirmed centrally. In Europe any commercially available CE marked device shall be used (for country specific requirements refer to Appendix E).

A variety of biospecimens including tumor tissue and blood will be collected at the times designated in the SoA (Table 1) and [Table 4](#) to perform IHC, NGS and cfDNA analysis in a central laboratory.

Confidential

Document State: Effective (Controlled)  
CONFIDENTIAL

Page 47 of 118

Predictive biomarkers of response or resistance to the investigational product will be explored, including but not limited to:

- IHC: Tumor specimens will be stained for the NICD1 and other biomarkers such as but not limited to PD-L1, Ki-67 and FBXW7.
- NGS: Mutational analysis will be performed in tumor tissue samples as well as in cfDNA.
- Pharmacodynamic biomarkers indicative of drug activity will be measured in blood such as but not limited to:
  - Genes regulated by Notch activity: HES-1, 5, 4, HEY-1, 2, HEYL, NRARP.
  - Angiogenesis biomarkers: HIF1 alpha, and VEGF.
  - Negative regulators: DTX1, FBXW7.

Tumor tissue for biomarker analysis will be required for study participation (block of 25 unstained slides required). Tumor biopsies will also be taken on-treatment at Cycle 4 Day 1 ±28 days.

Samples may be stored according to local regulations following the last participant's last visit for the study at a facility selected by the Sponsor to enable further analysis of biomarker responses to AL101.

The Laboratory Manual will provide details on biomarker sample collection.

**Table 4 Biomarker Blood Sample Collection**

Sample Type	Volume (mL)	Cycle	1					2	3	4	Odd 	EOS 
			Day	1	2	8	22					
		Time	Pre 	+7 h	+24-48 h	Pre	Pre	+7 h	+24-48 h	Pre	Biopsy 	pre
cfDNA	10		X						X	X	X	X
mRNA	2.5		X	X	X	X	X	X	X	X	X	X

Every additional odd cycle (starting Cycle 5)

End of Study

Pre-infusion

To be obtain on same day as on-treatment biopsy (to be collected on Cycle 4, Day 1 ±28 days)

#### 5.4.1 Stipulations for Tumor Biopsy

Patients must agree to provide two separate tumor biopsies, at screening and on-treatment at Cycle 4 Day 1 ±28 days (or earlier if the patient progressed). On-treatment biopsies do not need to be done if either the site investigator or person performing the biopsy judges that no tumor is accessible for biopsy or that biopsy poses too great of a risk to the patient. (If the only tumor accessible for biopsy is also the only lesion that can be used for RECIST v1.1 response evaluation, then the patient may be exempt from biopsy after discussion with the Sponsor).

Confidential

Document State: Effective (Controlled)  
 CONFIDENTIAL

Page 48 of 118

Attempts should be made to biopsy lesions which are not considered to be “target lesions” per RECIST 1.1. criteria.

## 6 INVESTIGATIONAL PRODUCT

### 6.1 INVESTIGATIONAL PRODUCT ADMINISTRATION

AL101 is a potent and selective inhibitor of gamma secretase-mediated Notch signaling. It will be administered as described in [Table 5](#).

**Table 5** Investigational product

Intervention Name	AL101
Type	Small Molecule
Dose Formulation	Solution for infusion
Unit Dose Strength(s)	mg/mL
Dosage Level(s)	1.2 mg/mL; 4 mg (Cohort 1) and 6 mg (Cohort 2) Frequency: Weekly (QW) on Days 1, 8, 15 and 22 of each 28-day cycle)
Route of Administration	AL101 will be administered using an IV infusion pump over 60 minutes; time windows of -5 minutes to +10 minutes are permitted. The connection between the tubing from the infusion pump to the patient should be close to the insertion of the intravenous catheter.  The exact duration of infusion should be recorded in both source documents and eCRFs. The start time of dose administration will be called “0” hour. If an infusion is extended, interrupted or discontinued prior to completion, the duration and the reason for any dose extension, interruption or discontinuation will be recorded in the eCRF.
Preparation	Cohort 1: Prior to IV administration, the drug product is diluted 3.3 mL (use 5mL syringe) in a 250 mL infusion bag of 0.9% Sodium Chloride Injection, USP (normal saline) or 5% Dextrose Injection, USP (D5W).  Cohort 2: Prior to IV administration, the drug product is diluted 5.0 mL (use 5 mL syringe) in a 250 mL infusion bag of 0.9% Sodium Chloride Injection, USP (normal saline) or 5% Dextrose Injection, USP (D5W).  Only diethylhexyl phthalate-free bags and sets can be used to administer solutions. Aseptic practices should be followed when handling, preparing, and administering the infusion solutions because the drug vial does not contain antibacterial preservatives or bacteriostatic agents. A sufficient excess of drug product is included in each vial to account for withdrawal losses.  Refer to Study Pharmacy Manual for more details.

Confidential

Document State: Effective (Controlled)  
CONFIDENTIAL

Page 49 of 118

Premedication Instructions	As with any medication containing Cremophor, use premedication per the institution guidelines to reduce risk of infusion reactions. For any questions, please contact the Sponsor's Medical Monitor.  Based on prior experience with Taxol (containing Cremophor)  ; these and/or other measures deemed medically necessary should be implemented based on the judgment of the Investigator. To reduce the risk of infusion reactions caused by Cremophor, premedication with H1- and H2-blockers (diphenhydramine and ranitidine or equivalents) or corticosteroids (refer to Section 7.1.2) will be given.
IMP definition	A new drug that is used in a clinical investigation (FDA)
Sourcing	AL101 is manufactured by Bristol-Myers Squibb.  Investigational product will be provided to the site centrally by the Sponsor or designated representative (Fisher Clinical Services, USA).
Packaging and Labeling	AL101 is supplied as a single-use sterile solution 5 mL per vial (1.2 mg/mL; equivalent of 6 mg per vial) for IV administration; The secondary packaging and labeling of investigational product will be performed by Fisher Clinical Services.  All packaging and labeling operations for investigational product will be performed according to Good Manufacturing Practices for Medicinal Products and the relevant regulatory requirements. Label text for the AL101 vial will at a minimum include the protocol number, the contents of the vial, lot number, storage conditions, and Sponsor name and address.
Former Name(s) or Alias(es)]	BMS-906024

For pre-medication instructions, refer to Section **Error! Reference source not found..**

Additional information is provided in the AL101 Study Pharmacy Manual.

## 6.2 METHOD OF ASSIGNING PATIENTS

This is an open-label design, with all patients assigned sequentially to 1 of 2 cohorts and receive AL101 monotherapy. Cohort 2 will be open for enrollment at each center after the current amendment is approved and Cohort 1 enrolled up to a maximum of 45 patients.

## 6.3 DISTRIBUTION AND SHIPMENT OF THE INVESTIGATIONAL PRODUCT

For detailed information on the distribution and receipt of investigational product please refer to the Study Pharmacy Manual.

The investigational product will be shipped under appropriate conditions with temperature monitoring device. Upon arrival at the clinical investigation site, the study pharmacist or designated team member should examine the investigational product supplies and report any

 Taxol (paclitaxel) label: [https://www.accessdata.fda.gov/drugsatfda\\_docs/label/2011/020262s049lbl.pdf](https://www.accessdata.fda.gov/drugsatfda_docs/label/2011/020262s049lbl.pdf)

discrepancies in amounts received, damaged supplies or temperature excursion immediately as outlined in the Study Pharmacy Manual.

Each shipment of investigational product supplies for the study will be accompanied by a shipment form describing the contents of the shipment, acknowledgement of receipt and other appropriate documentation. The study staff will confirm the receipt of clinical supply and will return signed drug accountability logs as instructed in the Study Pharmacy Manual.

All study supplies should arrive at the Pharmacy/Investigational site in sufficient quantity and in time to enable dosing as scheduled. Investigational product shipment will be done according to enrollment projections.

#### **6.4        STORAGE AND HANDLING OF THE INVESTIGATIONAL PRODUCT AT THE CLINICAL SITE**

Please refer to the Study Pharmacy Manual for AL101 preparation. Each drug kit will be labeled with the protocol number, storage information, warning language (i.e., as required by local legislation for investigational drug products), dosing and storage instructions. Immediately before dispensing investigational product, the dispensing study staff member will write on the label the patient's Study ID number.

The Investigator or the designated pharmacist (or other authorized designee) is responsible for ensuring that the appropriate storage conditions for the investigational products are maintained in accordance with the requirements in the Study Pharmacy Manual.

The study staff and monitors should also check the investigational product supplies to ensure sufficient amount of investigational product is on hand for active patients and that the supplies are not expired.

All investigational products must be kept in a locked area with access to the investigational product limited to designated study personnel. Only personnel under the supervision of either the Investigator or the local pharmacist are authorized to dispense investigational product. The Investigator is responsible for recording the receipt and use of all drugs supplied, and for ensuring the supervision of the storage and allocation of these supplies. Full accountability will be performed for all used and unused investigational product.

Investigational product should be stored as instructed per the IB.

#### **6.5        ACCOUNTABILITY AND COMPLIANCE OF INVESTIGATIONAL PRODUCT**

The Investigator or pharmacist/designee may dispense investigational product(s) for only patients enrolled in the study. Individual patient accountability records must be kept by the site staff. The patient number, the date, batch number/wallet number, and quantity of investigational product used or returned by the patient, as well as device and device components will be recorded on the appropriate accountability forms by the site staff. These records and the inventory of investigational product, device and device components on site will be verified by the study monitor for accuracy and completeness on an ongoing basis throughout the study. Unused drug supplies will be disposed of as instructed in the Study Pharmacy Manual.

---

ConfidentialDocument State: Effective (Controlled)  
CONFIDENTIAL

Page 51 of 118

Treatment compliance will be assessed at all visits during the study. It will be based on accountability records and an inventory of used/unused supplies.

At the end of the study, the monitor will conduct a final drug reconciliation for all patients and the study site overall. All records of investigational product administration, accountability records and drug disposition records will be examined and reconciled by the study monitor. Further details will be provided in the Study Pharmacy Manual.

## **6.6 DOSE MODIFICATION AND TOXICITY MANAGEMENT GUIDELINES**

Dose modification associated with AL101 is described below in [Table 6](#).

The causality assessment system proposed by the World Health Organization Collaborating Centre for International Drug Monitoring, the Uppsala Monitoring Center (WHO-UMC) will be used by the Investigator for assessing drug-related (certain, probable/likely, possible) non-hematological Grade 3 (except isolated Grade 3 electrolyte abnormality that are not associated with clinical signs or symptoms and are reversed with appropriate medical intervention within 48 hours) and hematological Grade 4 toxicities will lead to a 1 dose level reduction for AL101. For easily manageable Grade 1 or 2 toxicity, no dose reductions are required, but careful observation and treatment is required. Dose modification of intolerable Grade 2 toxicity will be evaluated on a case-by-case basis with the Sponsor. Re-escalation of the dose following a dose reduction is allowed only after discussion and approval of the Sponsor's Medical Monitor. Maximum AL101 treatment interruption allowed is 28 days; treatment interruption longer than 28 days will result in discontinuation of patient from the study. Additional treatment guidelines may be implemented by the Investigators, with agreement of the Sponsor/Medical Monitor, as needed to ensure patient safety.

 "The use of the WHO-UMC system for standardized case causality assessment" a communication by WHO-UMC in 2011; [https://www.who-umc.org/media/164200/who-umc-causality-assessment\\_new-logo.pdf](https://www.who-umc.org/media/164200/who-umc-causality-assessment_new-logo.pdf)

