#### 1.4.1 Dose Selection

The doses selected for this study, 4 mg QW (Cohort 1) and 6 mg QW (Cohort 2) are based on nonclinical studies, prior clinical studies conducted by BMS (the previous developer) (CA216001, CA216002 and CA216003) and preliminary outcome from the ongoing ACCURACY study. Please also refer to the IB for further information.

In Study CA216001, in dose escalation on a QW schedule, patients were treated at AL101 dose levels of 0.3 (n = 4), 0.6 (n = 3), 1.2 (n = 4), 2.4 (n = 4), 4 (n = 7), 6 (n = 14), and 8.4 mg (n = 11). In study CA216001, AL101 was safe and tolerated in doses up to 4 mg QW administration. DLTs were observed in the 6 mg and 8.4 mg dose levels. As AL101 potentially contributed to these DLTs and no DLTs were reported in the 7 DLT-evaluable patients treated at this dose in the dose escalation phase, the MTD in the solid tumor population treated on a QW dosing schedule as was recommended by the previous developer of AL101 to be 4 mg.

Overall, 43 patients were treated at a dose of 4 mg QW, in either the dose escalation (N=7) or dose expansion (N=36) phases. Treatment-related ≥Grade 3 AEs included hypophosphatemia

Confidential

Document State: Effective (Controlled)  
 CONFIDENTIAL

Page 31 of 118

(41.9%; 18/43), diarrhea (18.6%; 8/43), hypokalemia (7.0%; 3/43), and anaphylactic reaction, anemia, AST increased, nausea, pruritus, and vomiting (2.3% each; 1/43).

PK results from Study CA216001 indicate that AL101 exposure ( $C_{max}$  and AUC) increases approximately linearly for QW dosing from 4 mg to 6 mg.

PD results (Hes1 expression in PB) from Study CA216001 indicate greater maximum effect and duration of target inhibition when increasing the QW dose from 4 mg to 6 mg. Mean Hes1 inhibition is maintained greater than 50% throughout 7 day period at 6 mg, where it recovers to under 50% by day 7 at 4 mg.

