Any other AL101-related Grade 3 nonhematologic adverse event except electrolyte abnormalities that may be managed with supplements	Interrupt AL101 until resolution to $\leq$ Grade 1 and then resume at 1 dose level lower (i.e., 2.4 mg QW). If treatment interruption is longer than 28 days, the patient will be discontinued from the study (refer to Section 4.5 for early withdrawal of patients from therapy or assessment).	Interrupt AL101 until resolution to $\leq$ Grade 1 and then change dose regimen to 6 mg 2 weeks on / 1 week off for the first episode. Decrease dose to 4 mg QW for second episode and to 2.4 mg QW for third episode. If treatment interruption is longer than 28 days, the patient will be discontinued from the study (refer to Section 4.5 for early withdrawal of patients from therapy or assessment).

Confidential

 Document State: Effective (Controlled)  
 CONFIDENTIAL

Page 60 of 118

Dose Modification Criteria for AL101 -Related Adverse Events	AL101 modification	
	Note: for any questions, please contact the Sponsor's Medical Monitor.	
	Cohort 1 (4 mg QW IV)	Cohort 2 (6 mg QW IV)
Grade 4 non-hematologic AEs including Grade 4 non-hematologic lab abnormalities lasting > 72 hours	Permanently discontinue from IP (refer to Section 4.5 for early withdrawal of patients from therapy or assessment ).	Permanently discontinue from IP (refer to Section 4.5 for early withdrawal of patients from therapy or assessment ).

Confidential

 Document State: Effective (Controlled)  
 CONFIDENTIAL

Page 61 of 118

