c. Paired tumor biopsies (a resection, or core needle or punch biopsy with 20 gauge or larger and at least 2 passes) will be collected both at screening (fresh or archival within 3 years), and at Cycle 4 Day 1 ± 28 days or earlier if the patient progressed (fresh sample, provided medically safe and not contraindicated). If an archival tumor block or 25 unstained slides are not available, the patient will be required to have a fresh tumor sample obtained at screening. Attempts should be made to biopsy lesions which are not considered to be “target lesions” per RECIST 1.1. criteria.

d. Full physical examination at baseline; targeted physical examination at other time points.

e. Complete blood count (CBC) includes hemoglobin, hematocrit, platelet count, WBC count, and absolute differential count.

f. Chemistry includes glucose, blood urea nitrogen (BUN), creatinine, total bilirubin (a direct bilirubin should be obtained if the total bilirubin level is >1.5 times ULN), albumin, AST (SGOT), ALT (SGPT), alkaline phosphatase (ALP), lactate dehydrogenase, electrolytes (sodium, potassium, chloride, calcium, magnesium, and phosphorus). Creatinine clearance (CrCl) will be conducted at screening only; Calculation of CrCl will be based on acceptable institution standard. g. Screening laboratory may be used if conducted within 3-7 days of CID1.

h. Chemistry will be conducted every week for the first 3 cycles and then every 2 weeks, with the exception of liver function tests (AST/ALT/ALP/bilirubin) which will be done weekly until week 32, and then every 2 weeks thereafter.

i. Coagulation factors will be done on Day 1 of every other cycle (e.g., C3D1, C5D1...).

j. Urinalysis (specific gravity, pH, glucose, protein, ketones, and blood) performed at Screening and as clinically indicated.

k. In the event of possible abnormal ECG findings, per the discretion of the investigator, additional ECG reads could be added at follow-up visits. The ECG evaluation will be performed centrally. Clinically significant ECG abnormalities will be recorded on the eCRF. Triplicate ECGs, at least 3 minutes apart, will be performed if QTcF is > 500 msec or if the Investigator identifies an ECG finding (for example QT interval prolonged or cardiac arrhythmia) that is an adverse event and related to investigational product. l. Pre-menopausal female patients of childbearing potential only. Urine or serum pregnancy tests are acceptable.

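### Protocol Section 6.6 and Table 6 contradict each other on Grade 3 electrolyte abnormalities, and the 48-hour condition in Section 6.6 cannot be verified from scheduled chemistry

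*Protocol*

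**What the plan says.** **Protocol Section 6.6, running text.** Drug-related non-hematological Grade 3 toxicity "will lead to a 1 dose level reduction for AL101". Electrolytes are carved out in a parenthesis: "except isolated Grade 3 electrolyte abnormality that are not associated with clinical signs or symptoms", with the further condition that they "are reversed with appropriate medical intervention within 48 hours".

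**Protocol Table 6, row for remaining Grade 3 nonhematologic events.** The trigger reads "Any other AL101-related Grade 3 nonhematologic adverse event except electrolyte abnormalities that may be managed with supplements". If the row applies, AL101 is interrupted until Grade 1 or better. Cohort 1 then resumes at 2.4 mg QW. Cohort 2 moves to 6 mg two weeks on and one week off for a first episode, 4 mg QW for a second and 2.4 mg QW for a third.

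**Schedule.** SAP Section 6.2, note h, states "Chemistry will be conducted every week for the first 3 cycles and then every 2 weeks"; note h to Protocol Table 1 says the same. Only liver tests stay weekly to week 32. The panel includes potassium and phosphorus (Protocol Section 5.2.8). The on-treatment visit window is ±2 days.

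**Background rate.** Protocol Section 1.4.1, on 43 patients given 4 mg QW in the earlier Phase 1 solid-tumor study, says that treatment-related Grade 3 or higher "AEs included hypophosphatemia" at 18/43, followed by diarrhea at 8/43 and hypokalemia at 3/43.

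**The concern.** Both texts govern the same event, and neither yields to the other. A site that follows the running text and a site that follows the table can treat identical patients differently. The condition that separates the texts most often in practice is likely to be the 48-hour one, and the routine schedule does not generate the data needed to apply it.

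What is at stake is consistent application of a safety rule and the meaning of a reported result. SAP Section 7.8.1 tabulates patients with a planned reduction from 6 to 4 mg or from 4 to 2.4 mg, and that count depends in part on which text each site used. The event concerned was common in the earlier study.

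**Working it through.** **1. The two exemptions side by side.** Take a related Grade 3 electrolyte abnormality that supplements can manage.

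| Presentation | Section 6.6 | Table 6 |
|---|---|---|
| Isolated, no symptoms, reversed within 48 h | exempt | exempt |
| Isolated, no symptoms, reversed after 48 h | not exempt | exempt |
| With signs or symptoms | not exempt | exempt |
| Not isolated | not exempt | exempt |

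The texts agree in the first row only. Table 6's sole test is "except electrolyte abnormalities that may be managed with supplements".

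**2. The two consequences for a first non-exempt event.**
- Cohort 1: both texts lead to a one-level reduction, which Table 6 gives as 2.4 mg QW after interruption. The step is 1 − 2.4/4 = 40%.
- Cohort 2: Section 6.6 gives one dose level down, which other Table 6 rows show as 4 mg QW. Table 6 keeps 6 mg and changes the schedule. If each on-week carries one infusion, the Table 6 regimen averages 6 × 2/3 = 4 mg per week, the same planned weekly average as 4 mg QW. The dose per infusion, the schedule, the next step and whether the patient counts as a 6-to-4 mg reduction in SAP Section 7.8.1 all still differ.

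**3. Can scheduled chemistry show reversal within 48 hours?** Gap = (interval − window shifts) × 24 h.
- Weekly draws: nominal 7 × 24 = 168 h; one visit moved 2 days, 5 × 24 = 120 h; both moved toward each other, 3 × 24 = 72 h.
- Two-weekly draws: nominal 14 × 24 = 336 h; minimum 10 × 24 = 240 h.

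The shortest permitted gap, 72 h, exceeds 48 h. Two scheduled draws can therefore never show it.

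**4. Is a recheck required elsewhere?** Protocol Section 5 allows unscheduled laboratory tests at the investigator's discretion. The repeat-test rule in Section 8.1.1 covers abnormal values that are not clinically significant and sets no interval. The same section counts a value that requires therapy as clinically significant. No required draw remains.

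**5. How common is the event?** The Section 1.4.1 percentages reproduce: 18/43 = 41.9%, 8/43 = 18.6%, 3/43 = 7.0%. The Clopper-Pearson interval for 18/43 runs from the 2.5% point of Beta(18, 26) to the 97.5% point of Beta(19, 25), that is 27.0% to 57.9%. Hypophosphatemia was 18/8 = 2.25 times as frequent as the next listed event.

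For this trial, Protocol Section 1.3.2 reports 29 treated patients at the October 2019 cut-off. It lists the adverse events seen in more than 30% of them, regardless of causality: nausea, fatigue, diarrhea and vomiting. Hypophosphatemia is absent. Since 0.30 × 29 = 8.7, that implies at most 8/29 (27.6%) at any grade, if the list is complete.

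**The case against.** **Table 6 may be the operative list.** Section 6.6 opens by saying that dose modification is described in Table 6, and the table's header sends questions to the Sponsor's Medical Monitor. That is a fair argument and gives sites a route for doubt. It does not settle the matter. Section 6.6 goes on to state its own mandatory rule, no precedence is given, and a site that reads only one text has no reason to ask.

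**A schedule of activities is a minimum.** A site that treats Grade 3 hypophosphatemia may well recheck it, and Section 5 permits that. This stands: the 48-hour condition can be verified by an extra draw. It can also be seen to have failed when the abnormality is still present at the next visit. What remains is that no draw is required, so verification depends on local habit. It would go too far to say that Section 6.6 modifies every Grade 3 case and Table 6 none. That treats an unmeasured interval as a failure, which the text does not say.

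**The Grade 4 rule.** A reader might infer that permanent discontinuation at Grade 4 also depends on which text is followed, or that its 72-hour limit is equally unreadable. The documents do not support either inference. The criterion "Grade 4 non-hematologic lab abnormalities lasting > 72 hours" appears only in Table 6, identically for both cohorts; the Section 6.6 text covers non-hematological Grade 3 and hematological Grade 4. Grade 4 values on consecutive scheduled draws are evidence of persistence beyond 72 hours. Only the duration of an abnormality that resolved between draws is unknown.

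**Conclusion.** The contradiction is real and rests on plain text. A symptomatic, non-isolated or slower-to-correct Grade 3 electrolyte abnormality that supplements can manage is dose-modified under Section 6.6 and exempt under Table 6. For a non-exempt first episode in Cohort 2 the two texts also prescribe different actions. The 48-hour condition cannot be verified from scheduled chemistry alone.

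The number of patients affected cannot be derived from the documents. The 41.9% is from another study, at 4 mg QW, and pools Grade 3 with anything higher. The Grade 3 share, the rate at 6 mg and the rate in this trial are not given. A reader might apply 41.9% to the cohort maxima, giving 0.419 × 45 ≈ 19 and 0.419 × 42 ≈ 18 patients. That is not a supported forecast, because this trial's early 4 mg data imply at most 8/29 at any grade at that cut-off.

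A reader might also infer that the conflict distorts the comparison of 4 mg with 6 mg. The study is non-comparative, the SAP treats each cohort as an independent trial, and the exemption is worded alike for both cohorts. An effect on response results is not shown. The supported consequence is inconsistent application of a safety rule, which carries into the tabulated dose reductions.

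**What to change.** Reconcile the Section 6.6 text and the Table 6 row into one exemption and one consequence per cohort, worded identically in both places. If a time condition is kept, state how it is to be verified. Which exemption, which consequence and whether a time condition applies are for the sponsor to decide.

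The cost is wording in Section 6.6 and Table 6, plus a schedule note if verification is specified. If a time condition stays, affected patients may need one repeat chemistry sample. SAP Section 4 places the current SAP between the dry run and database lock, so the change may reach few patients in this trial. It still matters for anyone on treatment and for reading the dose-reduction summary.
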